8.1.1 Dose Limiting Toxicities

Definition of dose limiting toxicities (DLTs) based on CTCAE 4.0. All toxicities will be attributed to study drug (everolimus) except hematological toxicities. Hematological DLTs will be defined for the combination of eribulin and everolimus. If a hematological DLT occurs, dose reduction or delay will be conducted according to rules defined in 8.1.6 and 8.2.2.

DLT is defined as an AE or abnormal laboratory value as at least possibly related to the study medication and meets any of the criteria per CTCAE 4.0 . The following table is recommended for the most anticipated toxicities.

Decisions to escalate, de-escalate, or expand a dose level will be based on the first course of treatment. To be evaluable for toxicity, a patient must receive at least 1 complete course of treatment (at least 75% of planned dose of both drugs without toxicity) and be followed for at least 21 days (more if there is a dose delay) or have experienced a DLT as defined above. All patients enrolled are to be fully followed for toxicity; any patients who

are not evaluable for toxicity will be replaced. Intra-patient dose escalation is not allowed.

Table 8.1.1a Criteria for defining dose-limiting toxicities.

Toxicity	DLT criteria
Hematology	CTCAE grade ≥ 3 neutropenia lasting more than 7 consecutive days
	CTCAE grade 4 thrombocytopenia
	CTCAE grade 4 neutropenia
	CTCAE Grade 3 neutropenia with fever (temperature $\geq 38.5^{\circ}\text{C}$)
Non-hematology	Any CTCAE grade ≥ 3 AEs with the following exceptions
Exceptions to DLT criteria	Grade 3 alopecia
	Controllable grade 3 nausea and vomiting
	<5 days of CTCAE grade 3 fatigue
	Triglycerides $< 1,500\text{mg/dL}$, which recover within 1 week
	Grade 3 laboratory abnormalities that are correctable to grade 2 or less within 24 hours
	Grade 3 hyperglycemia that is controlled to Grade 2 and under should not be considered DLT. For management of hyperglycemia, please refer to section 8.1.9.
Treatment delays	>2 weeks as a result of unresolved toxicity during the first cycle of therapy (failure of ANC to recover to $\geq 1,000/\mu\text{L}$ or platelets to recover to $\geq 50,000/\mu\text{L}$ within 14 days of the last treatment)
Others	Failure to complete at least 75% of planned dose of either one of the drugs during cycle 1, due to toxicity, will also be considered a DLT.

Follow-up for toxicities.

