11.1 Design

11.1.1 Phase I portion

The Phase I portion of this study will use the toxicity equivalence range (TEQR) design of Blanchard and Longmate [35] to evaluate select dose levels of the everolimus in combination with eribulin and to determine the RP2D. In this implementation of the TEQR design, we define the target equivalence range of the DLT rate as 0.20-0.35. DLT rate levels of 0.51 or higher will be considered too toxic and doses that achieve that level will not be revisited. The dose escalation de-escalation rules will be the following. If the rate of participants that experience a DLT is below 0.20 we will escalate, if the rate is above 0.35 we will de-escalate and if it is between 0.20-0.35 we will stay at the current dose. Participants will enter the protocol in cohorts of 3. The starting dose will be dose level 1. This study will end when 12 research participants are studied at a single dose level with a toxicity level below 0.51. Further we also implement the additional rules: 1) terminate the trial if dose level 1 is too toxic, and 2) if the current dose is safe but based on the data the next dose is deemed too toxic, stay at the current dose. The RP2D will be the dose closest to target of 0.25 below 0.51 based on isotonic regression. The dose schedule is provided in Table 11.1 below.

The PMT team for protocol 14036 reviewed the data: dose level 2 was closed after 2 of 3 evaluable participants experienced DLTs an observed rate of 67%; dose level 1, we saw 4 DLTs in 8 evaluable participants giving an observed DLT rate of 50% on this dose. Our equivalence range for DLT rate for this trial is 20-35%, our observed rate of 50% is above 35% so we plan to de-escalate. Two participants experienced grade 4 neutrophil count decrease and 2 experienced mucositis (1 grade 3 DLT, 1 participant received 71% of Everolimus due to grade 2 which is a DLT). Thus, the team decided to amend the protocol to allow for two new dose levels at a lower dose of Eribulin, and start the next cohort of patients at dose level B1.

Table 11.1 Dosing Schedule: cycle length is 21 days

Dose level A	Everolimus (oral)	Eribulin (intravenous)
A-1	2.5mg daily (day 1 to 21)	1.4mg/m ² on days 1, 8
A1	5mg daily (day 1 to 21)	1.4mg/m ² on days 1,8
A2	7.5mg daily (day 1 to 21)	1.4mg/m ² on days 1,8
A3	10mg daily (day 1 to 21)	1.4mg/m ² on days 1, 8

Dose level B	Everolimus (oral)	Eribulin (intravenous)
B1	5mg daily (day 1 to 21)	1.1mg/m ² on days 1,8

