B-1	2.5mg daily (day 1 to 21)	1.1mg/m ² on days 1,8

Table 11.2 is a pictorial representation of the dose escalation/de-escalation guidelines for a target toxicity of 25% and $\varepsilon_1=5\%$ $\varepsilon_2=10\%$ giving an equivalence range of 20%-35%. The numbers of research participants treated at the current dose is provided in the columns and the number of research participants experiencing a DLT in the rows. Note that this design is similar to a 3+3 design for the first 3 patients seen at a dose as it escalates if 0 study participants experience DLTs, holds if 1 experiences a DLT (33%), and de-escalates if 2 experience a DLT, differing from a 3+3 at sample sizes of 6 and above patients as it holds at 33% toxicity and de-escalates at 36% toxicity or above.

Based on the results of 1,000 simulated trials considering 4 toxicity probability schedules (**Table 11.3**) for the 4 doses in combination with the trial specifications listed above, the median sample size was 18 with 95% confidence limits of 12 and 24 and the sample size

Table 11.2: Dose escalation/de-escalation guidelines (E= escalate, D=de-escalate, S=stay, DU=de-escalate and do not return to this dose).											
		Number of research participants treated on the current dose level (Standard sample size based on a cohort size =3 are bolded.)									
		3	4	5	6	7	8	9	10	11	12
Number of Research Participants Experiencing a DLT	0	E	E	E	E	E	E	E	E	E	E
	1	S	S	S	E	E	E	E	E	E	E
	2	DU	D	D	S	S	S	S	S	E	E
	3	DU	DU	DU	D	D	D	S	S	S	S
	4				DU	DU	D	D	D	D	S
	5						DU	DU	D	D	D
IRB Protocol No. 14036 2/1/2017	6							Version Date: DU	DU		D
Version: 13	7							Page 53 of 79			DU

at the MTD was ≥ 12 in at least 91% of trials. Note **Table 11.3** provides the rates at which each dose level for each schedule was chosen as the MTD (MTD rate) and the average number of research participants seen at each dose (Ave # Pts.).

Table 11.3: Associated rates each dose level is identified as the MTD and average number of patients studied for 4 dose toxicity probability scenarios						
Toxicity Probability Scenarios	Dose levels					No MTD
	-1	1	2	3		
Scenario 1	0.05	0.1	0.25	0.50		
RP2D rate	0.03	0.29	0.56	0.12		0
Ave # Pts.	0.4	5.9	8.1	3.6		
Scenario 2	0.025	0.05	0.20	0.40		
RP2D rate	0.01	0.15	0.58	0.27		0
Ave # Pts	0.08	4.7	8.2	5.8		
Scenario 3	0.025	0.05	0.1	0.25		
RP2D rate	0.01	0.05	0.27	0.66		0
Ave # Pts	0.12	3.8	5.6	9.1		
Scenario 4	0.1	0.25	0.4	0.5		
RP2D rate	0.19	0.55	0.22	0.04		.01
Ave # Pts	2.5	8.27	4.7	1.3		

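### As worded, the Phase I evaluability rule drops non-DLT patients who had any toxicity but keeps every DLT, which would bias the DLT rate upward if applied literally

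*Combined protocol and SAP*

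**What the plan says.** Section 8.1.1 bases dose decisions on the first course and defines who is evaluable for toxicity. There are two ways in:

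- the patient completed a course, explained in a parenthesis as "at least 75% of planned dose of both drugs without toxicity", and was followed for at least 21 days; or
- she must "or have experienced a DLT as defined above".

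Patients who "are not evaluable for toxicity will be replaced". The parenthesis gives no grade and does not say dose-limiting, although DLT is a defined term in the same sentence. No other section defines evaluability.

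Table 8.1.1a, in the same section, lists toxicities that are not DLTs, such as grade 3 alopecia, controllable grade 3 nausea and vomiting, and brief grade 3 fatigue. Its last row makes the following a DLT: "Failure to complete at least 75% of planned dose of either one of the drugs during cycle 1, due to toxicity".

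The rate among evaluable patients drives the design in section 11.1.1: "we define the target equivalence range of the DLT rate as 0.20-0.35". It goes on: "If the rate of participants that experience a DLT is below 0.20 we will escalate". Above 0.35 the trial de-escalates, and "DLT rate levels of 0.51 or higher will be considered too toxic".

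**The concern.** The two branches treat patients unequally. A DLT always keeps a patient in the count. A patient who takes full doses and has, say, grade 1 stomatitis meets neither branch as worded and is replaced. Only non-DLT patients can be lost, so the numerator is complete, the denominator shrinks and the bias has one direction.

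The wording also clashes with Table 8.1.1a. Its exceptions exist so that patients with those events count as not having had a DLT; under the literal rule they would not count at all. And because under-dosing caused by toxicity is already a DLT, the toxicity words in the parenthesis add nothing except this exclusion.

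At stake are the Phase I primary endpoint and every remaining escalate, stay or de-escalate call, including those on schedule B. Margins in Table 11.2 are narrow: 4 DLTs in 11 patients means de-escalate, 4 in 12 means stay.

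**Working it through.** **Inputs.** Target DLT rate 0.25, stay range 0.20–0.35 and too-toxic bound 0.51 (11.1.1). Level 1: 4 DLTs in 8 evaluable; level 2: 2 in 3 (11.1.1). 14 treated, 12 evaluable, and an allowance of 6 unevaluable or ineligible patients for the whole trial (11.2). The documents give no cycle 1 rate of any toxicity, so q, the share of non-DLT patients with any cycle 1 toxicity, is an assumption, taken over 0.2 to 0.7.

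**The plan's own figures.** The stated rules reproduce every legible cell of Table 11.2. A simulation of the stated design (cohorts of 3, stop at 12 on a dose, isotonic choice nearest 0.25; 10,000 trials per scenario) gives a median sample size of 18 in scenarios 1–3 and 15 in scenario 4, against the stated 18. Selection rates in scenario 1 are 0.03/0.28/0.60/0.09, against 0.03/0.29/0.56/0.12 in Table 11.3. Small gaps remain (the upper limit of the scenario 1 sample size is 27, against 24), because end-of-trial rules are not fully specified.

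**Bias under the literal rule.** With true rate p, the expected observed rate is p / [p + (1 − p)(1 − q)]. For p = 0.25:

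| q | Calculation | Reads |
|---|---|---|
| 0.2 | 0.25 / (0.25 + 0.600) | 0.29 |
| 0.44 | 0.25 / (0.25 + 0.420) | 0.37 |
| 0.5 | 0.25 / (0.25 + 0.375) | 0.40 |
| 0.7 | 0.25 / (0.25 + 0.225) | 0.53 |

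The reading passes a limit L when q > 1 − p(1 − L) / [L(1 − p)]:

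- L = 0.35: 1 − 0.1625/0.2625 = 0.38
- L = 0.51: 1 − 0.1225/0.3825 = 0.68

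For scale only, 8.1.2 gives stomatitis in 44%–70% of everolimus patients, mostly grade 1–2. That is not a cycle 1 figure. The same section cites 25% with a steroid rinse; q = 0.25 gives 0.25 / (0.25 + 0.5625) = 0.31. Other toxicities would add to either.

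**Effect on the design.** Scenario 1, where the third dose column is truly 0.25 (5,000 trials per q above 0):

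| q | Chance of choosing that dose | Mean enrolled | Mean evaluable | Mean replaced |
|---|---|---|---|---|
| 0 | 0.60 | 18.2 | 18.2 | 0 |
| 0.44 | 0.34 | 26.7 | 17.0 | 9.7 |
| 0.5 | 0.28 | 28.8 | 16.8 | 12.0 |
| 0.7 | 0.07 | 41.6 | 15.9 | 25.7 |

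**Was the rule applied literally?** Levels 1 and 2 hold 4 + 2 = 6 DLTs. If the one evaluable patient not listed by level (12 − 8 − 3 = 1) had no DLT, 14 − 6 = 8 patients were non-DLT, and 14 − 12 = 2 of them were not evaluable. If any toxicity triggered replacement, the binomial chance of 2 or fewer out of 8 is 0.24 at q = 0.44, (1 + 8 + 28)/256 = 0.14 at q = 0.5, 0.01 at q = 0.7 and below 0.001 at q = 0.9.

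**Do past decisions change?**

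- Level 1, both excluded patients restored: 4/10 = 0.40. Adding the unlisted patient too: 4/11 = 0.364. Both exceed 0.35, so de-escalation stands.
- Level 2, one or two restored: 2/4 = 0.50 or 2/5 = 0.40. The direction is unchanged, though both fall below 0.51, so Table 11.2 would read D rather than DU. The documents do not say at which level the two patients were treated.

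**The case against.** The strongest reply is that nobody would read the parenthesis literally. It sits in the DLT section, its alternative is having had a DLT, and Table 8.1.1a makes sense only if patients with non-DLT toxicity count. The natural sense is then 75% of dose delivered without dose-limiting toxicity. The allowance of 6 unevaluable or ineligible patients does not fit a rule that replaces everyone with a side effect, and 12 of 14 treated patients were in fact evaluable. This stands as evidence of intent. It does not settle the text: the reasons for the two exclusions are not given, the listed counts (8 + 3 = 11) do not match 12, and at moderate q a count of 2 in 8 is not improbable under literal use.

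Two stronger readings are tempting.

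- A reader might infer that the DLT rate that led to schedule B was inflated. The documents do not support this: they point to narrower use, and the level 1 call survives restoring every patient in question.
- A reader might use the 54.5% all-grade neutropenia in 10.7.1 as q and conclude that 25% reads 0.25 / (0.25 + 0.75 × 0.455) = 42%. But 54.5% is a share of all patients, not of non-DLT patients, and is not limited to cycle 1. Grade 4 neutropenia is itself a DLT. If every DLT patient were neutropenic, the reading is 0.25 / (0.25 + 0.455) = 35.5%, barely over the limit. With q = 0.545, a true 10% reads 0.10 / (0.10 + 0.90 × 0.455) = 19.6%, which still means escalate.

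**Conclusion.** The wording is defective and should be corrected. Followed as written, it removes only non-DLT patients, biases the DLT rate upward and contradicts Table 8.1.1a. A true 25% would read between 29% (q = 0.2) and 53% (q = 0.7), passing 35% once q exceeds about 0.38. These sizes rest on an assumed q and on literal use. The documents give no cycle 1 any-toxicity rate, and the trial's counts suggest that the words were not applied literally. No past dose decision is shown to be wrong. The case for acting is that the written rule governs the remaining dose decisions, and a reader cannot reproduce the denominator from it.

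**What to change.** In 8.1.1, replace the parenthesis with: *(at least 75% of the planned dose of both drugs) without a DLT*. Then state that the only non-evaluable patients, to be replaced, are those without a DLT who either miss more than 25% of either drug for reasons other than toxicity or are not followed for 21 days. Every patient then falls into one class, because missing more than 25% of a drug through toxicity is already a DLT in Table 8.1.1a. No dose and no DLT criterion changes.

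While the text is open, give the reasons for the two non-evaluable patients, reconcile 8 + 3 = 11 with the stated 12, and report the DLT rate among all treated patients as a sensitivity analysis.

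The cost is a sentence or two in 8.1.1 and a short check of records already held.

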8.1.2 Stomatitis

Inflammation of the mucous membranes in the mouth may occur. Ulcerated areas in the oral cavity, inner surface of the lips, or tongue, closely resembling aphthous stomatitis may occur. Onset typically occurs early (≤ 1 month after treatment initiation) and is

transient. 44%-70% of everolimus-treated patients develop mouth ulcers, stomatitis, or oral mucositis, which are mostly Grade 1 or 2.

To reduce dose-limiting oral mucositis, a **mandatory dexamethasone mouth wash (alcohol-free 0.5 mg/5 mL dexamethasone solution) will be used for primary prophylaxis of oral mucositis**. Steroid based mouth wash was studied in a randomized phase II study evaluating miracle mouth wash plus hydrocortisone versus prednisolone mouth rinses as prophylaxis for everolimus- associated stomatitis[37]. This study provided evidence of a reduced incidence of mTOR-associated stomatitis with prophylactic use of a steroid mouth rinse. The 25% incidence of all-grade and 8%/0% incidence of G2/3 stomatitis compare favorably with the 67% and 24%/8% incidence of all-grade and G2/3 stomatitis, respectively, in BOLERO-2. These preliminary data also demonstrated the safety and tolerability of these 2 steroid mouth rinses.

Currently, there is an ongoing phase II trial examining the effect of dexamethasone based mouth wash[38]. We would like to utilize this dexamethasone based mouth wash for the current study. The mouth care regimen consists of a steroid-based mouthwash (alcohol-free 0.5 mg/5 mL dexamethasone solution) . Patients will start the prophylactic oral care regimen on the same day they start treatment with everolimus + eribulin. The mouthwash should be taken as follow:

- Swish and spit 10ml of mouthwash 4 times each day
- Hold mouthwash in mouth for a minimum of 2 minutes
- Swish it around in the mouth, so it comes in contact with every surface of the mouth
- Spit it out (do not swallow)
- Abstain from eating or drinking for a least 1 hour after performing mouthwash regimen
- Continue with assigned oral care regimen for the first 2 months (56 days) of everolimus + eribulin therapy, after with mouthwash will be stopped.

Treating physician or other health provider of the treatment team will write the prescription of the steroid-based mouthwash. Usage of the mouth wash should be documented by patient and followed up during clinic visit.**After first two cycles of treatment, patient can use the steroid mouth wash 4 times a day as needed .**

Upon diagnosis of \geq grade 1 stomatitis, a normal saline (0.9% sodium chloride) mouth rinse will be added while patient is continuing the dexamethasone mouthwash. The normal saline is administered as a 10mL swish and spit (QID) (must be done prior to the steroid mouthwash QID). Patients administered normal saline (0.9% sodium chloride) mouth rinse (swish and spit), then waited for 10-15 mins, and then administered dexamethasone mouth wash. No dose adjustment is required for grade I stomatitis.

Dose adjustments for stomatitis

Grade	Symptom	Management	Everolimus Dose Adjustment
2	Symptomatic but can eat and swallow a modified diet.	
 Manage with topical analgesic mouth treatment (e.g. benzocaine, butyl aminobenzoate, tetracaine hydrochloride, menthol or phenol) with or without topical corticosteroids (i.e. triamcinolone oral paste). Avoid agents containing alcohol, hydrogen peroxide, iodine and thyme derivatives. 	
 Interrupt everolimus administration until resolution to \leq grade 1 or baseline grade / value. If resolution occurs within \leq 7 days, everolimus should be re-started at the dose level prior to interruption. If resolution takes >7 days, or if event recurs within 28 days, hold everolimus until recovery to \leq grade 1 or baseline grade / value and reintroduce everolimus at one dose level lower, if available. Patients will be withdrawn from the study if they fail to recover to \leq grade 1 or baseline grade / value within 28 days.
3	Symptomatic and unable to adequately eat or hydrate orally.	Same as above.	
 Temporary dose interruptions until recovery to Grade ≤ 1. Re-initiate everolimus at a lower dose.
4	Severe (symptoms are life threatening).		
 Discontinue everolimus and treat with appropriate medical therapy.

8.13 Rash

Rash is reported in 29%-59% of patients treated with everolimus. It may be erythematous maculopapular, acneiform, and eczematoid. Research participants should receive the following education about rashes:

- Inform research participant of the possibility of developing rash.
- Inform research participant to promptly report any signs or symptoms of rash to initiate treatment early.
- Educate research participants to employ good skin care including:
 - Moisturize frequently. Use a thick, alcohol-free emollient cream.
 - Take short lukewarm showers, using mild, moisturizing (fragrance-free) soap.

- Bathe in lukewarm water plus 1-2 cups of baking soda.
- Use a sunscreen of SPF 15 or higher, preferably containing zinc oxide or titanium dioxide (minimize sun exposure).

Dose adjustments for rash

Grade	Symptoms	Management	Everolimus Dose Modification
2	Moderate	
 Consider treatment with topical steroids, topical antibiotics and/or oral antihistamines 	
 Temporary dose interruptions until recovery to Grade ≤ 1. Re-initiate everolimus at the same dose. If rash recurs at Grade 2, interrupt dose until recover to Grade ≤ 1. Re-initiate everolimus at a lower dose.
3 (or intolerable grade 2 papulopustular)	Severe	
 Consider oral antibiotics 	
 Temporary dose interruptions until recovery to Grade ≤ 1. Re-initiate everolimus at a lower dose.
4	Life-Threatening		
 Discontinue everolimus and treat with appropriate medical therapy.

8.14 Non-infectious pneumonitis

Non-infectious pneumonitis is reported in 14%-19% of patients treated with everolimus. Incidence of Grade 3 and 4 non-infectious pneumonitis has been reported up to 4% and up to 0.2%, of patients respectively. Fatal outcomes have been observed.

Dose adjustments for non-infectious pneumonitis

Grade	Symptom	Management	Everolimus Dose Modification
2	Symptomatic, not interfering with ADL.	
 Rule out infection. Consider treatment with corticosteroids. 	
 Consider interruption of therapy until symptoms improve to Grade ≤ 1. Re-initiate everolimus at a lower dose. Discontinue treatment if failure to recover within 4 weeks.

3	Symptomatic, interfering with ADL, O_2 required.	
 Rule out infection. Consider treatment with corticosteroids. 	
 Consider interruption of therapy until symptoms improve to Grade ≤ 1. Re-initiate everolimus at a lower dose. If toxicity recurs a Grade 3, consider discontinuation.
4	Life threatening, ventilator support indicated.	
 Rule out infection. Consider treatment with corticosteroids. 	
 Discontinue everolimus.

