8.15 Dosing guidelines for everolimus-related non-hematologic toxicities

Toxicity	Action
Non-Infectious Pneumonitis	Please refer to table above.
AST or ALT elevation Grade 1 ($>$ ULN - 3.0 x ULN) Grade 2 ($>$ 3.0 - 5.0 x ULN)	Maintain current dose level
AST or ALT elevation Grade 3 ($>$ 5.0 - 20.0 ULN)*	
Interrupt everolimus administration until resolution to \leq grade 1 (or \leq grade 2 if baseline values were within the range of grade 2). If resolution occurs \leq 7 days, everolimus should be re-started at the dose level prior to interruption.
 
If resolution takes $>$ 7 days, or if event recurs within 28 days, hold everolimus until recovery to \leq grade 1 or baseline grade / value and reintroduce Everolimus at one dose level lower, if available.

AST or ALT elevation Grade 4 ($>$ 20 x ULN) Recurrence of grade 4 AST or ALT elevation after dose reduction or toxicity requiring Everolimus interruption for $>$ 28 days	
Interrupt everolimus administration until resolution to \leq grade 1 (or \leq grade 2 if baseline values were within the range of grade 2). If resolution occurs \leq 7 days, everolimus should be re-started at one dose level lower. If resolution takes $>$ 7 days, discontinue everolimus.
 
Discontinue everolimus.

Intolerable grade 2 mucositis, or grade 3 AE, except hyperglycemia or hypertriglyceridemia or hypercholesterolemia	
Interrupt everolimus administration until resolution to \leq grade 1 or baseline grade / value.
 
If resolution occurs within \leq 7 days, everolimus should be re-started at the dose level prior to interruption.
 
If resolution takes $>$ 7 days, or if event recurs within 28 days, hold everolimus until recovery to \leq grade 1 or baseline grade / value and reintroduce everolimus at one dose level lower, if available.
 
Patients will be withdrawn from the study if they fail to recover to \leq grade 1 or baseline grade / value within 28 days.

Toxicity	Action
Any other grade 4	Hold everolimus until recovery to grade ≤ 1 or baseline value. Reintroduce Everolimus at one dose level lower, if available.
Grade 3 or 4 clinical liver failure (asterixis or encephalopathy/coma)	Discontinue everolimus.

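### Grade 3 non-infectious pneumonitis has only an optional everolimus hold, so a patient who is not held meets no stopping limit, unlike a grade 2 patient

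*Combined protocol and SAP*

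**What the plan says.** The dose-adjustment table in Section 8.1.4 (printed as 8.14 in the body) has rows for grades 2, 3 and 4.

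- **Grades 2 and 3, hold:** both rows use the same wording, "Consider interruption of therapy until symptoms improve" to grade 1 or lower.
- **Grades 2 and 3, restart:** both rows say "Re-initiate everolimus at a lower dose".
- **Grade 2 only, non-recovery:** "Discontinue treatment if failure to recover within 4 weeks".
- **Grade 3 only, recurrence:** "If toxicity recurs a Grade 3, consider discontinuation". The row has no non-recovery limit.
- **Grade 4:** stop everolimus.

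The first row of the table in Section 8.1.5 is for non-infectious pneumonitis, and its action is "Please refer to table above". The last row of that table stops everolimus for any non-hematologic toxicity that needs an interruption of more than 28 days.

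Section 8.1.4 notes that fatal outcomes have occurred and gives the background rates: "Incidence of Grade 3 and 4 non-infectious pneumonitis has been reported up to 4% and up to 0.2%, of patients respectively".

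**The concern.** Grade 3 here means symptoms that limit daily activities and a need for oxygen. The table treats this state less strictly than grade 2 in one respect. The grade 2 limit runs from failure to recover, so it applies whether or not everolimus was held. Grade 3 has no matching line, and the hold that would bring the 28-day rule of 8.1.5 into play is left to judgement.

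An investigator could therefore keep giving everolimus to a patient with unresolved, oxygen-requiring pneumonitis beyond 4 weeks and still be within the protocol. The same investigator would have to stop a milder case at 4 weeks. What is at stake is patient safety in a few cases. This point covers everolimus only; the handling of eribulin was not assessed.

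**Working it through.** The plan gives no figure to reproduce. The check compares the rules and then counts how many patients they could touch.

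**Step 1. Which table governs.** The pneumonitis row of 8.1.5 sends the reader to 8.1.4 and has no grade restriction. Section 8.1.4 therefore governs grade 3.

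**Step 2. How other grade 3 events are held.**

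| Grade 3 event | Place | Everolimus hold |
|---|---|---|
| Stomatitis | 8.1.2 | Required |
| Rash | 8.1.3 | Required |
| AST/ALT elevation | 8.1.5 | Required |
| General grade 3 row | 8.1.5 | Required |
| Non-infectious pneumonitis | 8.1.4 | To be considered |

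The grade 3 stomatitis and rash rows also print no time limit. That matters less, because their hold is mandatory and so the 28-day row of 8.1.5 will apply to a prolonged case. For pneumonitis the optional hold is what opens the gap.

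**Step 3. What happens if there is no recovery by 4 weeks.**

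| | Everolimus held | Everolimus not held |
|---|---|---|
| Grade 2 | Stop (own row; also last row of 8.1.5 once past 28 days) | Stop (own row) |
| Grade 3 | Stop once past 28 days (last row of 8.1.5) | No stop printed |

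Only the lower right cell is open. An unheld case that improves to grade 2 would arguably come under the grade 2 row, so the open cell mainly concerns cases that stay at grade 3.

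**Step 4. Number of grade 3 cases.** Inputs:

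- Upper reported grade 3 rate of 4% (8.1.4).
- Grade 3-4 rate of 3% with everolimus 10 mg daily plus exemestane (1.2.2).
- 27 patients at the RP2D (11.1.2).
- Planned maximum of 45, with 14 already treated when schedule B was added (11.2). Places left: 45 − 14 = 31 at most.

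Expected cases are n × p, and the chance of at least one is 1 − (1 − p)^n.

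| n | p | Expected cases | Chance of at least one |
|---|---|---|---|
| 27 | 0.04 | 27 × 0.04 = 1.08 | 1 − 0.96^27 = 0.67 |
| 31 | 0.04 | 31 × 0.04 = 1.24 | 1 − 0.96^31 = 0.72 |
| 27 | 0.03 | 27 × 0.03 = 0.81 | 1 − 0.97^27 = 0.56 |
| 31 | 0.03 | 31 × 0.03 = 0.93 | 1 − 0.97^31 = 0.61 |

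These are expected counts of all grade 3 cases, not bounds. The optional hold bears on each of them. The missing limit bears only on those not held and not recovered at 4 weeks, a fraction for which the documents give no rate.

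**Step 5. Effect on the design.** Under Table 8.1.1a a grade 3 non-hematologic event in cycle 1 is a DLT unless listed as an exception, and pneumonitis is not listed. Whether everolimus was held does not alter that count. The 4-month EFS rule does not use the hold either.

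**The case against.** **The wording is ordinary clinical discretion.** The same phrase is used at grade 2, the instruction to restart at a lower dose presupposes a hold, and a careful clinician would hold the drug in a patient on oxygen. Section 9.2 also lets the investigator stop treatment for a serious event that cannot be tolerated or controlled. All of this stands, and it is why the point is small. But these provisions permit a stop, whereas at grade 2 a stop at 4 weeks is required.

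**The 28-day row of 8.1.5 already supplies the limit.** This is right for any patient whose everolimus is held, so it would be wrong to say that grade 3 pneumonitis has no limit at all. It does not reach a patient who is never held.

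**A stronger reading is tempting.** The general grade 3 row of 8.1.5 covers "Intolerable grade 2 mucositis, or grade 3 AE, except hyperglycemia or hypertriglyceridemia or hypercholesterolemia", and pneumonitis is not among those exceptions. That row requires a hold, withdraws patients not recovered within 28 days, and after resolution within 7 days says "everolimus should be re-started at the dose level prior to interruption". A reader might infer that it competes with 8.1.4 on hold, limit and restart dose, and that the protocol leaves the conflict open. The documents do not support this. The pneumonitis row refers the event to 8.1.4. Grade 3 AST/ALT elevation and grade 3 clinical liver failure likewise have their own rows without being excepted from the general row. If the general row overrode them, liver failure, for which everolimus must be stopped, could lead to a restart at full dose. The table makes sense only if the specific row prevails, so the restart dose for pneumonitis is the lower one.

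**Conclusion.** The point holds for the grade 3 row of 8.1.4 alone. The hold is optional where comparable grade 3 events require one, and a grade 3 case that is not held has no non-recovery stop although a grade 2 case does. This is a cheap improvement to a safety rule, not a flaw in the design.

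Roughly one grade 3 case is to be expected: 1.1 in 27 patients or 1.2 in 31 at 4%, and 0.8 or 0.9 at 3%. These counts assume that the background rates carry over. The 4% is an upper reported figure and the 3% comes from 10 mg daily, whereas schedule B uses 5 or 2.5 mg. The documents give no rate for the combination with eribulin, so the true figure could lie on either side.

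**What to change.** In the grade 3 row of Section 8.1.4:

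- Replace the optional hold with a direct instruction to interrupt everolimus until recovery to grade 1 or lower.
- Add that everolimus is discontinued if the event has not recovered to grade 1 or lower within 4 weeks. This agrees with the 28-day row at the end of 8.1.5.
- Keep the restart at a lower dose.

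Section 8.1.5 needs no change, since its pneumonitis row already points to 8.1.4. The cost is one row of wording in an amendment, with no extra visits, tests or patients. The downside is slightly less investigator discretion at grade 3.
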